7.0 Risks

Because of the reported risk of aerosolizing the virus with rinses, no hospitalized patients will be enrolled in the study. Additionally, patients in the study will be strictly directed to perform nasal saline irrigations in a separate bathroom/room in their house to prevent exposure to household contacts. If they are unable to accommodate these instructions, they will be excluded/removed from the trial. All patients who test positive for COVID-19 at VUMC are instructed to strictly self-quarantine and isolate themselves from friends, family, and acquaintances. Therefore, the restrictions of this study are not a substantial imposition on the ability of patients to keep themselves and their families safe.

There are reports of transient anosmia (loss of smell) in patients undergoing nasal saline irrigations with surfactant, though larger scale studies have not evaluated this and patients typically recovered once irrigations were discontinued.

While an absolute percentage is unknown, estimates have reported an average of 16 deaths per year in the United States secondary to amoebic meningitis, though saline irrigation or CPAP use in this population is also unclear. Many of the deaths related to amoebic meningitis in the United States are presumed secondary to swimming and diving. There are extremely rare and isolated reports of amoebic meningitis in patients using nasal saline irrigations or continuous positive airway (CPAP) masks. Because of this risk, the FDA has recommended using boiled water (3-5 minutes) or water passed through a filter with an absolute pore size of 1 micron or smaller (either purchased or filtered at home). Use of appropriately treated water in saline rinses renders the risk of infectious meningitis vanishingly small. Johnson's Baby Shampoo is often added as an adjunct to rinses in the dosage of 0.5 teaspoons per rinse bottle. There are no known significant toxicities to this common adjunct to nasal saline, although patients have been noted in prior studies (PMID: 17405780, 23710951) to complain of the taste of shampoo in the back of the nose.

The medical records of the patients in this study will be accessed to ensure that they have not undergone inpatient hospitalization at VUMC during the course of the study. All data will be stored on encrypted, HIPPA compliant VUMC Box accounts for management and analysis. Data will not be exported in an unencrypted format. All KSP for the study have been trained in data safety and data management.

8.0 Reporting of Adverse Events or Unanticipated Problems involving Risk to Participants or Others

Any adverse risks will be reported immediately to Vanderbilt IRB and the Institution Biosafety Committee. If any AEs occurred, they would be reported to the Vanderbilt HRPP as required per institutional policy. Contact information for HRPP is as follow:

Human Research Protections Program [name] On campus: [name] [contact]

9.0 Study Withdrawal/Discontinuation

Any patients that wish to be withdrawn from the study can do so at any time. Any patients that initiate other intranasal medications or therapies outside of the study protocol will also be withdrawn. Additionally, any patient hospitalized during the trial period will have that hospitalization as their individual end point for the study.

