6.0 Study Procedures

Day 0: Patient tests positive for COVID-19 via nasal swab which is identified through Epic and is given information about the trial via telephone call. At that time, they may determine whether or not they would like to be enrolled in the study. Those enrolled in the study will be randomly assigned into one of 3 groups (control, intervention 1, intervention 2) using REDCap and delivered a package containing: nasal swabs with premeasured depth for insertion, saline rinse bottle with saline packets and detailed instruction guide (intervention 1, 2), Johnson's Baby Shampoo (Johnson & Johnson Inc., New Brunswick, NJ) for use with saline rinses (intervention 2), and symptom questionnaire/temperature sheets.

Days 1-21: Patients in intervention group 1 and 2 will perform nasal saline irrigations +/- ½ teaspoon of Johnson's Baby Shampoo in the morning and the evening. All patients will perform nasal swabs every 2-3 days (*See Instruction Sheet*). In the intervention arms, these swabs should be taken at least 4 hours after saline rinses are performed. Patients will also check temperature (at same time each day) and fill out a symptom questionnaire (*See Symptom Questionnaire*). At the completion of week 3, patients will call our team to collect swabs and questionnaire/temperature sheets. The paper questionnaires will be transferred to REDcap for data collection and analysis.

*The timing of the study is based on when patient initially tests positive for COVID-19 and is a rolling enrollment rather than simultaneously performed.

Once 90 (~30 per group) patients have completed their 21 days of swabs/temperature checks/questionnaires, the study trial will be completed and data analysis will be performed. Interim analysis will be performed at 45 total patients.

As these patients will be under quarantine for COVID-19 infection, they will receive and provide their swabs, temperature and symptom scoring sheets from their home address at the beginning and at the conclusion of the 21-day study period. The swabs will be collected using OMR 110, DNA Genoteck Inc, Canada, that will immediately neutralize virus due to isotonic detergents present in the buffer, at the same time stabilizing the DNA and RNA for further analysis. Study administrators will wear appropriate personal protective equipment when retrieving the above-mentioned specimens.

Laboratory and Analytic Methods

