10.0 Statistical Considerations

As this is a pilot study for the use of nasal saline irrigations in the COVID-19 patient population, a true power analysis is not possible. This study will use a truncated initial sample size of 90 patients spread across 3 intervention arms to ensure that exclusion of true outliers is possible. Data will be analyzed with routine statistical software, with a planned 95% confidence interval for statistical testing.

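### Early leavers have no stated specimen retrieval and no stated place in the analysis, so the Aim 2 arm comparison tends towards those who stayed

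*Combined protocol and SAP*

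**What the plan says.** Section 9.0 gives three ways for a randomised patient's participation to end early.

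- Own choice: "Any patients that wish to be withdrawn from the study can do so at any time".
- Starting another nasal treatment: "Any patients that initiate other intranasal medications or therapies outside of the study protocol will also be withdrawn". The withdrawal is from the study, not only from the rinses.
- Admission: "any patient hospitalized during the trial period will have that hospitalization as their individual end point for the study". Nothing is added on how the admission, or the data before it, enter the analysis.

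Section 6.0 sets the sampling: "All patients will perform nasal swabs every 2-3 days". Specimens and diaries stay in the home until the end: "At the completion of week 3, patients will call our team to collect swabs and questionnaire/temperature sheets". The same section places both hand-overs "from their home address at the beginning and at the conclusion of the 21-day study period".

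Section 6.0 starts the analysis when 90 patients, about 30 per group, have completed 21 days, and puts an interim analysis at 45 patients in total. Section 10.0 speaks of a "truncated initial sample size of 90 patients" chosen "to ensure that exclusion of true outliers is possible", and adds only standard software and a 95% confidence level. Neither section names an analysis population, a use for incomplete series or a method for missing swabs.

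**The concern.** Section 9.0 removes patients for something they do after randomisation. Section 6.0 then describes no way for the swabs they have already taken to reach the laboratory. Viral load, inflammation and bacterial load in Specific Aim 2 are measured from swabs, so an early leaver may contribute nothing to the arm comparison. An analysis population can still be written down late, provided results are unseen. A swab that was never collected cannot be recovered.

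Loss that differs by arm and tracks illness is plausible from the documents, though not shown. Controls receive no rinse, while Section 1.0 notes that saline can be bought without prescription, and a control who starts it would be withdrawn. The rinse arms carry a twice-daily task, and Section 7.0 reports shampoo taste and temporary loss of smell with the surfactant. Section 1.0 links a high nasal viral load to worse disease, so leaving because of illness could be related to the outcome. These routes act on different arms and may partly cancel.

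**Working it through.** **The plan's own figure.** 90 / 3 = 30 per arm, which agrees with Section 6.0. The plan gives no effect size, SD, power or dropout rate, so there is nothing else to reproduce.

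**What an early leaver holds.** One swab every 2-3 days for 21 days is 21/3 = 7 to 21/2 = 10.5, so 7 to 10 swabs. By day 8 (an example) it is 8/3 = 2.7 to 8/2 = 4, so about 2 to 4 swabs. Section 6.0 describes no step that retrieves these before the end of week 3.

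**Possible size of the bias (illustration).** All inputs here are assumptions: 5% loss in one arm and 10%, 20% or 30% in another; correlation (rho) of 0.3 to 0.7 between the tendency to leave and the outcome; no true effect; 30 analysed per arm; two-sided 5% test.

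If the upper fraction p of a normal selection variable leaves, the mean of that variable among those who remain falls by

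m(p) = phi(z) / (1 - p), where z is the upper-p normal quantile.

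- m(0.05) = 0.1031/0.95 = 0.109
- m(0.10) = 0.1755/0.90 = 0.195
- m(0.20) = 0.2800/0.80 = 0.350
- m(0.30) = 0.3477/0.70 = 0.497

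Shift in the arm difference = rho x [m(p) - m(0.05)], in SD units. The standard error of a difference is sqrt(2/30) = 0.258 SD. The false-positive rate comes from a noncentral t with 58 df and noncentrality shift/0.258.

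| Loss | m(p) - m(0.05) | Shift, rho 0.3 | Shift, rho 0.7 | False-positive rate |
|---|---|---|---|---|
| 10% vs 5% | 0.086 | 0.026 | 0.061 | 5.1% to 5.6% |
| 20% vs 5% | 0.241 | 0.072 | 0.169 | 5.9% to 9.9% |
| 30% vs 5% | 0.388 | 0.116 | 0.272 | 7.3% to 17.7% |

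The 17.7% uses the shift rounded to 0.27; the unrounded value gives 17.9%.

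**Sensitivity to the selection model.** With leaving modelled as logistic in the outcome (odds ratio 1.5 to 3 per SD), the shifts are 0.020-0.047, 0.059-0.134 and 0.098-0.219 SD for the same three loss patterns. They are of the same order and somewhat smaller at the top.

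**When there is no bias.** The shift is zero if rho = 0 (odds ratio 1), or if loss is alike across arms in rate and selection. Only precision is then lost.

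**The case against.** The best reply is that this is a pilot without a power analysis, that Aims 1 and 3 are descriptive, and that silence is not a rule. Much of that stands. Retention of data and collection at withdrawal might be covered in the consent pages, the telephone script or the instruction sheet, none of which was available. Nothing forbids an earlier pickup, and the collection device stabilises the nucleic acid. The pilot label does not remove the point: three arms are randomised, statistical testing is planned and Aim 2 compares arms.

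Several stronger readings are tempting, and the documents do not support them.

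- **That the plan specifies a completer analysis.** The 90 completers in Section 6.0 say when analysis starts, not who is in it.
- **That leavers' swabs are discarded.** No section says so; their loss is a risk that follows from silence.
- **That hospitalised patients are dropped.** The wording in Section 9.0 may well mean that follow-up ends with earlier data kept. It does not say.
- **That the separate-room rule in Section 7.0 drives loss from the rinse arms.** Section 4.0 applies it mostly at eligibility and extends it to swabs, which controls also take.
- **That outliers will be removed after the data are seen.** Section 10.0 says only that the sample size leaves room for exclusion. It gives neither rule nor timing.
- **That the meaning of 90 is unknown.** Section 6.0 says completed. Only the initial 90 in Section 10.0 and the interim count of 45 need reconciling with it.

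The higher false-positive rates need both correlation 0.7 and 20-30% loss against 5%. At correlation 0.3 they are 5.9% and 7.3%.

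**Conclusion.** The point holds as a gap that should be fixed. The supplied text withdraws randomised patients for post-randomisation behaviour, describes retrieval only at the end, and gives early leavers no place in the analysis. Following it as written makes those who stayed the patients most likely to be compared.

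Whether this biases Aim 2 depends on whether leaving is related to arm and outcome, which the documents cannot show. With a modest imbalance (10% versus 5%) the effect is negligible: at most 0.06 SD, under a quarter of the 0.258 SD standard error. It becomes material only with large imbalance and strong selection, reaching 0.27 SD at the edge of the assumed range. Confidence in the omission is high, subject to the pages not seen. Confidence in its consequence is moderate at best.

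**What to change.** 1. Separate stopping the assigned intervention from stopping data collection. Patients withdrawn under Section 9.0 are asked, with consent, to continue swabs and diaries to day 21.
2. For anyone who ends data collection early, including by hospitalisation, the study team makes contact and, with consent, retrieves the swabs and diaries already completed. Those who continue keep the usual week-3 pickup.
3. Make the primary comparison all randomised patients in their assigned arm, using all data obtained in a longitudinal repeated-measures model that accepts incomplete series, without removal of outliers. A completer analysis, and any outlier-excluded analysis under a rule fixed in advance, are secondary. Such a model assumes that loss is explained by the data observed, so item 4 is needed beside it.
4. Report hospitalisation, and withdrawals with reasons, by arm. Ask about admission to any hospital, since the record checks in Sections 7.0 and 11.0 cover VUMC only.
5. Minor: reconcile the initial 90 in Section 10.0 and the interim 45 with the 90 completed in Section 6.0.

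The cost is wording in the protocol, consent and analysis sections, plus one contact and possibly one early pickup per leaver. At an assumed 10-30% loss, 90 completers need 90/0.90 = 100 to 90/0.70 = 129 randomised, so 10 to 39 leavers; those who go on swabbing need no early pickup. The arm contrast may be somewhat diluted by patients who start other therapy, which the completer analysis helps to show. The clinical rules on stopping the intervention are not judged here.

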10.0 Statistical Considerations

As this is a pilot study for the use of nasal saline irrigations in the COVID-19 patient population, a true power analysis is not possible. This study will use a truncated initial sample size of 90 patients spread across 3 intervention arms to ensure that exclusion of true outliers is possible. Data will be analyzed with routine statistical software, with a planned 95% confidence interval for statistical testing.

11.0 Privacy/Confidentiality Issues

The medical records of the patients in this study will be accessed to ensure that they have not undergone inpatient hospitalization at VUMC during the course of the study, as well as to ensure positive COVID-19 testing. All data will be stored on encrypted, HIPPA compliant VUMC Box accounts for management and analysis. Data will not be exported in an unencrypted format. All KSP for the study have been trained in data safety and

data management. There will be no protected health information used for analysis or publication.

12.0 Follow-up and Record Retention

The estimated study duration is 12 months including data retrieval and data analysis. Following completion of the study, the data stored within the encrypted VUMC Box files will be deleted.
